### 5.5 Subject Discontinuation

Each registered subject shall remain in the trial until completion of the required follow-up period, however, a subject's participation in any clinical trial is voluntary and the subject has the right to withdraw at any time without penalty or loss of benefit. Conceivable reasons for discontinuation may include, but not be limited to, the following:

- Subject death
- Subject voluntary withdrawal
- Subject lost-to-follow-up as described below
- Subject's follow-up is terminated according to **Section 5.6 - Early Termination of the Clinical Trial**

The Sponsor must be notified of the reason(s) for subject discontinuation. The site will provide this information to the Sponsor. Investigators must also report this to their respective IRB/EC as defined by their institution's procedure(s).

No additional follow-up will be required or data recorded from subjects once withdrawn from the trial, except for the status (deceased/alive), which will be obtained from the Social Security Death Index.

However, if a subject withdraws from the trial due to problems related to the safety or effectiveness of the investigational device, the investigator shall ask for the subject's permission to follow his/her status/condition outside of the clinical investigation.

In case of subject withdrawal of consent, the site should make attempts to schedule the subject for a final clinical investigation visit. At this final follow-up visit, the subject will undergo the following assessments:

- Transthoracic echocardiogram
- Six-minute walk test
- Kansas City Cardiomyopathy Questionnaire
- Any assessments required to complete the Follow Up eCRF
- Any assessments required to complete the Adverse Event or Device Deficiency eCRFs, if applicable

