#### ***2.2.7 Description of the Control Group Device Used in the Randomized Cohort***

Subjects randomized to the Control group in the randomized cohort will receive TEER with the commercially-approved MitraClip system. Prior to randomization, the anatomic suitability for using MitraClip will be initially proposed by the local site heart team with the final determination made by the SEC in order to ensure concordance with the recently published criteria by the Heart Valve Collaboratory [66].

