#### 3.1 Primary Endpoints

##### 3.1.1 *Primary Composite Endpoint - Randomized Cohort*

The primary composite endpoint is: freedom from all-cause mortality and heart failure hospitalization at 12 months post index procedure. The composite endpoint will evaluate whether the Tendyne device is non-inferior to TEER with MitraClip.

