### ***12.7.5 Follow-up Compliance***

The Sponsor will work with investigational sites to maintain high follow-up compliance. The following strategies may be used for increasing compliance:

- During site initiation and training, the Sponsor will emphasize the importance of subject follow-up to the site, and that the site should communicate this importance to each subject.
- Sites will be informed to promptly reschedule any missed subject visits, and to reinforce the necessity of a follow-up visit.
- If a scheduled visit is missed due to subject illness, transportation issues, or travel, the site will be advised to:

- Reinforce the necessity of follow-up visits;
- Identify alternate transportation sources, and involve the Sponsor if necessary
- Sites will be instructed to ask subjects who withdraw during the trial to provide the reason for withdrawal and ask them if the investigator may contact them at the end of the trial follow-up.
- Subject follow-up rates will be monitored closely so that problems may be identified and addressed as soon as possible.
- For subjects who are lost-to-follow-up, sites may be requested to examine the Social Security Death Index to determine subject survival status (only the status will be sent to Sponsor, not any subject identifying information).

In addition to aforementioned steps, investigational sites will be educated on the importance of maintaining low rates of withdrawals for all registered subjects, including those that have been designated as a roll-in, and will be expected to make every effort to maintain low withdrawals during trial conduct. Withdrawals from the trial will require discussion between the investigator and the Sponsor.

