2.2.3 Survival Analyses

Survival analysis will be conducted to analyze time-to-event variables. Subjects without events will be censored at their last known event-free time point when they stay in the study. Survival curves will be constructed using Kaplan-Meier estimates.

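### Data recording stops at withdrawal except for vital status, so heart failure hospitalizations between withdrawal and 12 months are missing from the primary endpoint in every cohort

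*Protocol*

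**What the plan says.** All four cohorts share one primary endpoint, "freedom from all-cause mortality and heart failure hospitalization at 12 months post index procedure" (Protocol 3.1.1 to 3.1.4). In the Randomized cohort the secondary safety endpoint adds mitral valve reintervention by 12 months (Protocol 3.2).

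Protocol 5.5 then sets the rule for subjects who leave: "No additional follow-up will be required or data recorded from subjects once withdrawn from the trial". The one exception is whether the subject is alive or dead. The same section tells sites to try to arrange a final visit when consent is withdrawn, with echocardiogram, walk test, KCCQ and the follow-up and adverse event forms.

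Section 5.5 also has a clause for the case "if a subject withdraws from the trial due to problems related to the safety or effectiveness of the investigational device". Then "the investigator shall ask for the subject's permission to follow his/her status/condition outside of the clinical investigation". Protocol 2.2.1 defines the investigational device as Tendyne. Control subjects "will receive TEER with the commercially-approved MitraClip system" (2.2.7).

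Protocol 12.7.5 has sites ask withdrawing subjects for their reason and "ask them if the investigator may contact them at the end of the trial follow-up". That is a 60-month horizon.

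On analysis, SAP 2.2.3 says: "Subjects without events will be censored at their last known event-free time point when they stay in the study". Protocol 10.2.2 censors event-free Non-repairable subjects at the last available information, and SAP Appendix VI (VI.2.11) censors event-free Severe MAC CAP subjects at study exit.

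**The concern.** The primary endpoint has two components, and the protocol pursues only one of them after withdrawal. Death is still sought; heart failure hospitalization is not, even by telephone or chart review. Mitral reintervention is lost in the same way for the Randomized safety endpoint.

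A subject who withdraws at month 3 and is hospitalized for heart failure at month 6 is analysed as event-free to month 3 and then censored. That is harmless only if withdrawers have the same later risk as those who stay. The trial is open-label to site staff (Protocol 12.7), and the protocol itself describes the Tendyne procedure as the more invasive of the two (2.1.8). Withdrawal that is related to prognosis, and unequal between arms, is therefore plausible, though nothing in the documents shows how often it will occur.

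At stake are the Randomized non-inferiority comparison with its 12.5-point margin and the single-arm tests against goals of 45% (Non-repairable) and 43% (Severe MAC). The single-arm tests have no control group in which a similar bias could offset the first.

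**Working it through.** **1. Do the provisions, read together, recover the missing events?**

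- Final visit (5.5): captures events up to the visit, not later ones.
- Contact under 12.7.5: falls at the end of follow-up rather than at 12 months, does not say that hospitalizations are collected, and conflicts with the no-data rule in 5.5.
- Contact with a relative or general practitioner (5.5.1): serves vital status only.
- Permission clause in 5.5: the follow-up is outside the trial, and nothing sends it to the Clinical Events Committee (CEC) or the endpoint data.

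None of them gives hospitalization status from withdrawal to 12 months.

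**2. Does the recording rule differ by arm?** No. The no-data rule and the final visit apply to every subject. Only the permission clause, read literally, is specific to Tendyne. Sections 8.1 and 8.2 name both the Tendyne and the Control device where both are meant. Because the clause leads to follow-up outside the trial, it leaves the analysed data unchanged.

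**3. How large could the bias be?** The plan gives no figure to reproduce. The public text shows no withdrawal rate, expected event rate or dropout allowance. What follows is an illustration on assumed inputs.

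Let *w* be the share of an arm that withdraws early, S_s the 12-month event-free rate of those who stay and S_w that of withdrawers. The true rate is (1 − w)·S_s + w·S_w. Censoring at a very early withdrawal estimates S_s. Hence

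bias = S_s − [(1 − w)·S_s + w·S_w] = w × (S_s − S_w) = w × excess event risk of withdrawers.

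Assume *w* = 5 to 10% on Tendyne and 2% on Control, with an excess of 20 to 30 points in both arms. With 382/2 = 191 subjects per arm, that is about 10 to 19 Tendyne and 4 Control withdrawals.

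| | Low | High |
|---|---|---|
| Tendyne | 0.05 × 20 = 1.0 | 0.10 × 30 = 3.0 |
| Control | 0.02 × 20 = 0.4 | 0.02 × 30 = 0.6 |
| Net, towards Tendyne (points) | 0.6 | 2.4 |
| Share of 12.5-point margin | 0.6/12.5 = 4.8% | 2.4/12.5 = 19.2% |

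Other assumptions give other answers:

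- Equal withdrawal and equal excess in both arms: (w − w) × excess = 0.
- 10% on Tendyne and 5% on Control, excess 10 to 30 points: 0.05 × 10 = 0.5 to 0.05 × 30 = 1.5 points.
- The first set with the arms swapped: the same size, towards Control.

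In a single-arm cohort there is nothing to subtract. The same 5 to 10% and 20 to 30 points would overstate the event-free rate by 1.0 to 3.0 points against the 45% or 43% goal.

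The formula treats a withdrawer's whole year as unobserved, so for a given excess it overstates the effect of later withdrawals. Deaths found through the vital-status check would reduce it further if they count as events; the visible text does not say whether they do.

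**The case against.** The strongest case against the point is that the protocol already limits the damage and that several stronger readings fail.

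- A reader might infer that only subjects who leave because of Tendyne are asked about later contact. Section 12.7.5 puts that question to withdrawing subjects without limit by arm or reason.
- A reader might infer that all hospitalization data are lost for withdrawers. Events before withdrawal are kept, and the final visit can capture events to that date.
- A reader might infer that endpoint data are collected differently by arm. The recording rule is the same, and Protocol 12.7.2 keeps the follow-up schedule identical. The cohorts other than the Randomized cohort have no control arm at all.
- A reader might infer that a subject randomized to Tendyne who declines the procedure leaves the trial for the commercial control device. Section 8.1 keeps randomized subjects in follow-up if they are not implanted or the implant fails, and 8.2 keeps them after later cardiac procedures, with or without explant. These are not withdrawals, although the right to withdraw remains.

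It is also fair to say that the ITT definition, most of the missing-data text and the tipping-point appendix are redacted, so one cannot conclude that the plan ignores missing outcomes or that the ITT comparison is broken. SAP 2.2.3 is a general methods statement.

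All of this stands and narrows the point. It does not remove it. A sensitivity analysis can show how much uncollected events might matter, but it cannot recover them.

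**Conclusion.** The point holds in a limited form. Section 5.5 stops recording at withdrawal except for vital status, in both arms and all cohorts, so heart failure hospitalizations and mitral reinterventions from then to 12 months are not collected. Sections 5.5 and 12.7.5 conflict and need reconciling. Censoring can bias the Randomized comparison if withdrawal is informative and unequal across arms, in frequency or in excess risk. It can bias the single-arm tests if withdrawal is informative at all.

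The size and direction are unknown. The 0.6 to 2.4 points, or about 5 to 19% of the margin, rests wholly on assumed withdrawal rates and excess risk. The documents do not support a claim that the result will favour Tendyne. The Tendyne-only permission clause is a separate wording asymmetry in the Randomized cohort with no visible effect on the endpoint data. The case for change rests on its low cost, not on a demonstrated bias.

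**What to change.** Amend Protocol 5.5 and 12.7.5 together:

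- Separate stopping study visits from withdrawing consent to data collection.
- Ask every withdrawing subject, in the same way in both arms and all cohorts and whatever the reason, for permission for telephone contact and medical-record review within the trial through at least 12 months.
- Record deaths, heart failure hospitalizations and mitral reinterventions found this way in the trial database and send them for CEC adjudication.
- In 12.7.5, add contact at 12 months to the contact at the end of follow-up, and remove the conflict with the no-data rule.
- Reword the permission clause to name the Tendyne or Control device.

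The cost is a protocol and consent-form change and a small number of calls or record reviews. Protocol 8.2 already allows remote contact in rare instances. Some subjects will still refuse, so the gap will shrink but not close.

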#### **5.5.1 *Subject Lost to Follow-up***

If a subject misses two consecutive required follow-up visits and attempts to contact the subject as detailed below are unsuccessful, then the subject is considered lost to follow-up. Site personnel shall make all reasonable efforts to locate and communicate with the subject (and document these efforts in the source documents), including the following:

- A minimum of two (2) telephone calls, or e-mails, on different days over the specified follow-up window to contact the subject shall be recorded in the source documentation, including date, time and initials of site personnel trying to make contact.
- If these attempts are unsuccessful, a letter (certified if applicable) will be sent to the subject.
- If a subject misses one or more non-consecutive follow-up visits it will be considered a missed visit. The subject may then return for subsequent visits. If the subject misses two consecutive time points and the above-mentioned attempts at communicating with the subject are unsuccessful, the subject will be considered lost-to-follow-up.

**Note:** Contact with a general practitioner, non-trial cardiologist or relative will be considered subject contact for the purpose of collecting vital status information. The center shall retain records of the contact.

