## **8 FOLLOW-UP FOR EVALUATION OF SAFETY AND EFFECTIVENESS**

### **8.1 Clinical Follow-up (All Registered / Roll-in Subjects)**

Follow-up evaluations are required at 30 days, 3 months, 6 months, 12 months, and annually thereafter through 5 years (**Table 3**). For all registered and roll-in subjects, follow-up visits will be calculated from the date of the index procedure, or the date of registration if a subject is registered but does not undergo a procedure. Follow-up assessments can be performed at any point in the window, and should be conducted, whenever possible, by the same individual who performed the baseline tests. For a complete schedule of trial assessments occurring at each visit, refer to **Appendix IV: Trial Assessment and Follow-up Schedule**.

Subjects shall be followed at the investigational site where the subject was registered (or designated as a roll-in), and may be followed at another investigational site only with prior agreement from both the new site's Principal Investigator and approval from the Sponsor.

All registered and roll-in subjects should continue to be monitored and treated per applicable standards of care consistent with the subject's condition. Subjects should be followed by the site

investigators at all scheduled follow-up visits. Subjects implanted with the Tendyne or Control device must also be evaluated for device function.

During follow-up, the site Principal Investigator should collaborate with the other site investigators, as applicable, in determining the treatment strategy for all roll-in and registered subjects at their site. Any treatment during follow-up (e.g., due to an adverse event or a change in the subject's condition) should be reported on the appropriate eCRFs.

**Note:** If a subject has an unsuccessful Tendyne or Control device implant, they should remain in the trial and continue to be followed per the trial follow-up schedule. Additionally, if a subject is randomized to receive either the Treatment or Control device but does not undergo the implant procedure, they should remain in the trial and continue to be followed per the trial follow-up schedule (calculated from the date of randomization).

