## 8.2 30 Day, 3 Month, 6 Month, and Annual Visits

Follow-up visits are required at 30 days, 3 months (phone contact), 6 months, and annually thereafter through 5 years. Subjects must continue to take baseline medications without change during follow-up, unless clinically (medically) necessary. If there are any cardiovascular medication changes, these changes, and the reason for change must be documented on the eCRF. Required tests and procedures are outlined in **Appendix IV: Trial Assessment and Follow-up Schedule**. All visits and tests must be completed within the visit window specified in **Table 3**, even if the subject is in hospital. The following data will be collected for site visits:

- A physical exam including an assessment of subject's cardiac status and sitting vital signs (heart rate and blood pressure).
- Changes in concomitant cardiovascular medications (e.g., heart failure, hypertension, antithrombotic medications)
- NYHA Functional Classification assessment
- Blood tests performed, including: BNP or NT-proBNP, plasma free hemoglobin, serum creatinine, INR, CK-MB if indicated or Troponin (Type I or T) if indicated
- TTE
- 12-lead ECG
- Cardiac CT (**Note:** Only required at 30-day visit)
- KCCQ, SF-12, and EQ-5D questionnaires
- 6-Minute Walk Test
- Modified Rankin Scale (Assessment to be completed after suspected onset of stroke)
- Assess and record adverse events, if applicable
- Assess and record protocol deviations, if applicable
- COVID-19 assessment, if applicable

**Note:** The 3-month visit will be conducted via telephone. This visit will assess potential adverse events and changes to concomitant cardiovascular medications.

Echocardiography images (TTE) obtained at each follow-up visit should be submitted in a timely manner. Throughout the course of the trial, the Echocardiography Core Laboratory may provide feedback to sites regarding quality of images obtained.

During the follow-up period, if a subject requires a cardiac procedure (i.e., MV surgery, permanent LVAD, heart transplant), which may or may not result in explant of the Tendyne or Control device, the subject will remain in the trial and continue to be followed.

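### Lost-to-follow-up status can be assigned from day 120, before the 12-month endpoint, and no route is then stated for learning of heart failure hospitalization or mitral reintervention

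*Protocol*

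**What the plan says.** Protocol 5.5.1 states the rule twice, first as "If a subject misses two consecutive required follow-up visits and attempts to contact the subject as detailed below are unsuccessful" and again at the end of its list as "If the subject misses two consecutive time points and the above-mentioned attempts at communicating with the subject are unsuccessful". The steps listed under it are "A minimum of two (2) telephone calls, or e-mails, on different days over the specified follow-up window", followed by "If these attempts are unsuccessful, a letter (certified if applicable) will be sent to the subject". They sit under a general duty on sites to make all reasonable efforts, so they are a floor.

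Section 5.5 gives, among its reasons for discontinuation, "Subject lost-to-follow-up as described below". The visits that count are set by 8.1 ("Follow-up evaluations are required at 30 days, 3 months, 6 months, 12 months, and annually thereafter through 5 years") and by 8.2 ("Follow-up visits are required at 30 days, 3 months (phone contact), 6 months, and annually thereafter through 5 years"), so the 3-month telephone contact is a required time point.

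On return, 5.5.1 says "The subject may then return for subsequent visits", but that sentence follows the one on non-consecutive misses.

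After a subject is declared lost, two provisions apply, and both concern survival. The note in 5.5.1 accepts contact with a general practitioner, an outside cardiologist or a relative for vital status. Section 12.7.5 says sites may be asked to check the Social Security Death Index.

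**The concern.** The primary endpoint in every cohort is freedom from all-cause death and heart failure hospitalization at 12 months. The Randomized cohort's safety endpoint adds mitral reintervention. A subject declared lost at day 120 or day 212 has not reached the endpoint time, and the stated follow-up routes from then on cover death only.

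Event-free subjects are censored at the last time they were known to be event-free (SAP 2.2.3; Protocol 10.2.2 for the Non-repairable cohort). That is harmless only if being lost is unrelated to risk. The protocol itself describes candidates for this procedure as usually high risk, with comorbidities and frailty (2.1.6), so the assumption is open to question.

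If lost subjects do carry more risk, the event-free rate would come out too high. In the Non-repairable and Severe MAC cohorts it is compared with fixed goals of 45% and 43%, and no control arm would share the error. In the Randomized cohort, where site staff know the assignment, the comparison would be affected if loss differed by arm.

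**Working it through.** **1. Reproduce Table 3** (target day plus or minus the stated allowance).
- 30-day visit closes: 30 + 14 = day 44.
- 3-month call closes: 90 + 30 = day 120.
- 6-month visit closes: 182 + 30 = day 212.
- 12-month visit: opens 365 − 30 = day 335, closes 365 + 30 = day 395.

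All four agree with the table.

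**2. Earliest declaration** = close of the second of two consecutive missed windows, with contact also failing.

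| Pair missed | Rule can be met | To 12-month opening (335) | To target (365) | To close (395) |
|---|---|---|---|---|
| 30 days and 3 months | day 120 | 215 days | 245 days | 275 days |
| 3 and 6 months | day 212 | 123 days | 153 days | 183 days |
| 6 and 12 months | day 395 | none | none | 0 |

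In the first case 245/365 = 67% of the endpoint year lies after the declaration.

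**3. Points that move these dates.** Section 4.3 lists pre-discharge among the required evaluations. If it counted as a time point, the earliest date would be day 44; I do not rely on that reading. In the Randomized cohort, 10.1.1 counts follow-up from registration, while Table 3 counts from the procedure. With the procedure on day 14 after randomization, day 120 becomes day 134, which leaves 365 − 134 = 231 days. The censoring date is the last known event-free time, so it may precede the declaration. A subject who missed both early contacts might be censored near discharge.

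**4. What can still be learned after the declaration.**

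| Event | Stated route |
|---|---|
| Death | Practitioner, cardiologist or relative (5.5.1); optional index check (12.7.5) |
| Heart failure hospitalization | None specific to lost subjects |
| Mitral reintervention | None specific to lost subjects |

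The death route is permissive. It names one index, although sites are planned in the U.S., Canada, Europe and Japan (4.2).

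**5. Illustration of size (assumptions, not document figures).** Let s be the share lost before 12 months and e their excess 12-month event risk over retained subjects. If none of the excess is observed, the overstatement is s × e.
- s = 3%, e = 20 points: 0.03 × 20 = 0.6 points.
- s = 6%, e = 30 points: 0.06 × 30 = 1.8 points.
- Shares of 3–6% are about 11–23 of 382, 10–20 of 325 and 3–6 of 103 subjects.

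For any chosen s and e the product is nearer an upper bound than an estimate, because events seen before loss and deaths recovered afterwards both reduce it.

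**The case against.** Several parts of the opposing case stand.

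- A reader might infer that no later event is sought at all. That is wrong for death, one of the two primary components, which has the routes above.
- A reader might infer that two missed visits suffice. They do not: contact must also fail, and the listed steps are a minimum. Section 8.2 allows remote contact, and 12.7.5 adds rescheduling, transport help and monitoring of follow-up rates.
- A reader might take the statement in 5.5 that no further data are recorded as covering these subjects. It is written for subjects who have withdrawn. Whether it extends to those lost is not stated, so an end to data collection is partly an inference. No sentence forbids a lost subject from returning.
- A reader might conclude that the rule favours the device. The documents give no evidence that unreachable subjects are sicker. Frailty that prevents travel does not explain a missed telephone call.
- A reader might say that the analysis ignores the problem. SAP 2.3.1.1 refers to sensitivity analyses for missing data, and the text of SAP 2.9 and the tipping-point appendix is redacted, so that cannot be said.

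Two further arguments carry less weight. Serious adverse events are collected through trial completion (9.4.1) and may be found in medical records (9.4.2), but that general duty does not tell a site to look for events in someone it has stopped contacting. It is also true that changing the label alone would not move a censoring date. Renewed contact could, though the documents do not show how often it would succeed.

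**Conclusion.** The point holds in a limited form. Sections 5.5, 5.5.1, 8.1 and Table 3 together allow an unreachable subject to be declared lost, and so open to discontinuation, 215 or 123 days before the 12-month window opens. From then on the protocol states a route for vital status only. It is silent on heart failure hospitalization, on mitral reintervention and on renewed contact at 6 or 12 months.

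The dates are exact. The bias is conditional: it needs lost subjects to be at higher risk or, in the Randomized cohort, loss to differ by arm. The expected number lost is not visible, so the 0.6–1.8 points rest wholly on the assumed inputs and should not be read as a forecast. A redacted sensitivity analysis may bound the effect, but no analysis can recover events that were never collected. This is an inexpensive improvement worth making, and it does not show that the primary result would be invalid.

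**What to change.** Amend 5.5.1 as follows.

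1. Lost-to-follow-up status is not final for the primary endpoint until the 12-month window closes on day 395.
2. After two consecutive misses, the contact sequence is repeated at each scheduled time point up to then.
3. A subject who is reached may resume visits, and hospitalizations and mitral reinterventions in the interval are collected from medical records.
4. The note on practitioners, cardiologists and relatives covers heart failure hospitalization and mitral reintervention as well as vital status, within the subject's consent.

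The cost is a short amendment, which under 12.3 needs regulatory approval and documented IRB/EC acknowledgement or approval, at up to 80 sites, and a few extra calls for each out-of-contact subject. No visits or subjects are added.
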